(baseline), 2) immediately after surgery in the post-anesthesia care unit (PACU), 3) on postoperative day 2 (POD 2), and 4) one-month after surgery. We will also collect a single baseline blood sample on 120 participants in a non-surgical comparison group. During the baseline assessment, three green top tubes (30 cc) will be collected. At all follow-up time points, two green top tubes (20 cc) will be collected. Blood samples will be collected via peripheral venipuncture or central venous line (if available in the PACU and on POD 2). Blood samples will be collected into sterile vacuum tubes using either a vacutainer or butterfly system, at the preference of the phlebotomist. Every attempt will be made to “piggyback” our blood collection on clinically scheduled blood draws. For participants being assessed at home, blood will be drawn by a trained member of our research team. All collected blood will be centrifuged to separate plasma from cellular products, divided into small samples, and frozen at -80C for future use.

A.4.2. Biomarker discovery methods

Using these samples, at the end of year 2 we will create a matched longitudinal biomarker discovery sample of 50 surgical participants with delirium and 50 matched surgical participants without delirium. In year 4 of our study we will create an independent biomarker validation sample of 100 surgical participants (50 with delirium and 50 matched controls without delirium). Using the biomarker discovery sample, we will describe a cytokine “signature” for delirium using the Luminex multiplex analyzer system that simultaneously measures 28 plasma cytokines. We will confirm this cytokine signature in the discovery sample and validate it in the biomarker validation sample using Enzyme – linked Immunosorbant Assays (ELISA). Similarly, using the biomarker discovery sample, we will use quantitative mass spectrometry proteomics to describe a plasma protein “signature” for delirium. We will perform two validations: first, using proteomics in the biomarker validation sample, and then using ELISA in the combined discovery and validation samples. Using the combined biomarker discovery and validation samples, we will examine the relationship of the cytokine and protein signatures for delirium with cognitive and functional outcomes up to 18 months after non-cardiac surgery.

A.4.3. Measurement of the Apo E allele

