Nicotinamide adenine dinucleotide (NAD) function: The [name] lab will explore differences in oxidative functioning particularly in relationship to NAD function. The [name] lab (BIDMC) will assess inflammatory markers.

Generation of iPSCs: The HSCI iPSC Core Facility will derive and characterize iPSC lines on a fee-for-service basis. The iPSC Core has extensive experience in iPSC derivation from human blood using all current methods of reprogramming. The Core offers both derivation and characterization services so that the appropriate quality control measures can be put in place to ensure quality iPSC lines. The [name] and [name] labs will maintain the primary iPSC lines. The intent will be to eventually deposit these iPSC lines in a biorepository that has experience with banking and distributing human pluripotent stem cells. These labs have considerable experience in the manipulation and analysis of iPSC lines. We anticipate that these iPSC lines will be a valuable resource not only for this study but for the aging research community at large.

Table 3. Overview of Project Hypotheses and Analytic Approaches.

Project	Aim or Hypothesis	Outcome(s)	Predictor(s)	Approach(es)	NSC	Effect of Interest
1	Aim 1-2	Cognitive decline	Delirium Delirium Severity	GLMM	*	Time by delirium interaction
	Aim 3	Functional decline and health care utilization	Delirium	GLMM	*	Time by delirium interaction
2	Aim 1	Delirium	Cytokine signature	PCA, CLR		Cytokine profile dif. by delirium
	Aim 2	Delirium	Protein signature	SVM, PCA, CLR		Protein profile dif. by delirium
	Aim 3	Cognitive, functional decline	Cytokine/Protein signature Fractional CSF	GLMM	o	Reg. of change on predictor
3	H 1.1	Delirium incidence	volume	GLM		Reg. of outcome on predictor
	H 1.2	Delirium incidence	WMH volume	GLM		Reg. of outcome on predictor
	H 1.3	Delirium incidence	Global blood flow	GLM		Reg. of outcome on predictor
	H 2.1-3	Change in neuroimaging marker [‡]	Delirium	GLMM		Reg. of outcome on predictor
	H 3.1-2	Neuroimaging marker [‡]	GCP Biomarker signature	GLM		Reg. of outcome on predictor
	H 3.3	Delirium incidence, Cognitive decline	Neuroimaging marker x Cognitive Reserve [†]	GLMM	o	Effect modification of neuroimaging marker [‡] x Cognitive reserve [†]
4	Aim 2, H 1	Delirium incidence Cognitive, Functional	Reserve [†]	GLM, DTS	*	Reg. of outcome on predictor
	Aim 3, H 2-3	decline	Reserve [†]	GLMM, LGC		Reg. of outcome on predictor

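### Project 2's second validation of the protein signature reuses the patients in whom the signature was found, so it is not independent replication

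*Protocol*

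**What the plan says.** Protocol A.4.2 (Biomarker discovery methods) sets up two samples: a "matched longitudinal biomarker discovery sample of 50 surgical participants with delirium and 50 matched surgical participants without delirium", and an "independent biomarker validation sample of 100 surgical participants (50 with delirium and 50 matched controls without delirium").

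The cytokine and protein signatures are then handled differently.

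- Cytokines, by ELISA: "We will confirm this cytokine signature in the discovery sample and validate it in the biomarker validation sample".
- Proteins, found by mass spectrometry in the discovery sample: "We will perform two validations: first, using proteomics in the biomarker validation sample", "and" being followed by the second step, "then using ELISA in the combined discovery and validation samples".

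For cytokines, re-assay of the discovery patients is thus kept apart from validation in new patients. For proteins, the two sets of patients are pooled and the pooled result counts as a validation.

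**The concern.** A validation should show that the signature holds in patients who had no part in choosing it. In the pooled ELISA step, 100 of the 200 patients did have a part. Proteins enter the signature because they differed between the delirium groups in those 100 patients, partly by chance. ELISA on plasma from the same patients measures the same chance difference again, less whatever disagreement there is between the two assays. It can show that the mass spectrometry reading was technically right. It cannot show that the difference exists outside the discovery sample.

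Two things are at stake. The pooled ELISA effect size would be too large when quoted as a validated estimate. And a signature reported as validated twice would look better replicated than it is, because the second result is largely fixed by the discovery result and the first validation.

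**Working it through.** **Inputs.** Discovery 50:50 and validation 50:50 (A.4.2); two-sided alpha 0.05 (B.1.2). The protocol gives neither the number of proteins screened nor the agreement between mass spectrometry and ELISA. Both are assumed here: K = 100 independent null proteins, and correlation r between the two assays' test statistics in the same patients of 0.8 to 1.0. The matching factors are not modelled.

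**The plan's own figure.** B.1.2 gives 0.57 SD as detectable with 80% power in 50:50 without within-pair correlation. A two-sample t-test at 0.57 SD has power 0.806, and the exact detectable difference is 0.566 SD. The figure reproduces, so the 50:50 layout is read correctly.

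**Form of the pooled test.** Let z1 and z2 be the proteomics statistics in the discovery and validation samples. The ELISA statistics are e1 = r·z1 + √(1−r²)·noise and e2 = r·z2 + √(1−r²)·noise. The samples are of equal size, so the pooled ELISA statistic is (e1 + e2)/√2, and it passes if it exceeds 1.96 in absolute value.

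**Null protein, best of 100 in discovery.** By simulation the largest |z1| averages about 2.75.

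- r = 1: to pass, z2 must exceed 1.96·√2 − 2.75 = 2.77 − 2.75 = 0.02, which happens about 49% of the time. Simulation: 49%.
- r = 0.8: e1 averages 0.8 × 2.75 = 2.20, and the remaining spread is √(0.36 + 1) = 1.17. The required margin is (2.77 − 2.20)/1.17 = 0.49, giving about 31%. Simulation: 32%.
- Validation patients alone: 5% in either case.

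Other values of K in the same simulation, for r = 0.8 to 1.0:

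| Null proteins screened (K) | Pooled pass rate |
|---|---|
| 50 | 26-40% |
| 100 | 32-49% |
| 200 | 37-57% |
| 500 | 44-67% |

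If a protein is instead chosen simply because p<0.05 in discovery, the pooled pass rate is 34% at r = 1, 28% at 0.9, 18% at 0.7 and 12% at 0.5.

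**Null protein that has already passed the proteomics validation.** Take p<0.05 in the same direction as in discovery. At r = 1, two statistics above 1.96 pool to at least (1.96 + 1.96)/√2 = 2.77, so the pooled test cannot fail. For the best of 100, the simulated pass rate is 92% at r = 0.8, 99% at 0.9 and 100% at 1. With the simple p<0.05 selection it is 98% at r = 0.9, about 85% at 0.8 and 68% at 0.7.

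**Effect size when the protein is real (r = 1, selected at z1 > 1.96).** The standard error with 50 per group is √(2/50) = 0.20. For a true difference of 0.30 SD, the selection cut is 1.96 − 0.30/0.20 = 0.46. The mean of a standard normal above 0.46 is 1.11. The discovery estimate therefore averages 0.30 + 0.20 × 1.11 = 0.52, and the pooled estimate (0.52 + 0.30)/2 = 0.41. For a true 0.57 SD the same steps give 0.64 in discovery and 0.60 pooled. The validation sample alone returns 0.30 and 0.57.

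**The case against.** The strongest reply is that the pooled ELISA does not stand alone. It follows a proteomics validation in independent patients. A best-of-100 null protein passes that step in the same direction about 2.5% of the time, and passes both steps no more often than that. This stands. A reader might take 32-49% as the chance that Project 2 announces a false protein. The documents do not support that, because the figure applies only to the pooled step taken on its own. The protocol states no formal rule that a protein must pass the first step to reach the second, but the order is clear. The reply does not rescue the pooled step as evidence: if the first validation has done the work, the second almost repeats it.

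A reader might also infer that the whole of Project 2 is validated optimistically. It is not. The cytokine ELISA validation and the proteomics validation both use the independent sample alone, so the count of 28 cytokines has no place in this calculation.

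A third tempting reading concerns the long-term outcomes, for which A.4.2 uses the same pooled 200 patients: "we will examine the relationship of the cytokine and protein signatures for delirium with cognitive and functional outcomes up to 18 months". Half of that sample is delirious, against an assumed rate of at least 25% in the cohort (A.3.2.3.1), so one could claim an inflated slope of decline on the signature. The documents do not support this as a finding. Table 3 gives only GLMM and "Reg. of change on predictor", and B.2 presents the table as a brief outline. The protocol is silent on weighting and on adjustment for delirium; it does not state an unweighted, unadjusted model. Any distortion also depends on the target. It is zero if delirium does not affect the outcome, and it is absent if delirium is in the model and the direct signature effect is wanted. With an assumed odds ratio of 2 per SD and a delirium effect of −0.61 SD, the slopes are −0.071 (cohort) and −0.094 (1:1 sample) without a direct effect, or −0.274 and −0.296 with a direct effect of −0.2. That matter is not part of this point.

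**Conclusion.** The point holds for one step: the ELISA validation of the protein signature in the combined samples. It is fixed in the protocol text and is not independent replication. With 100 null proteins assumed and assay correlation 0.8-1.0, the pooled test passes the best null protein 32-49% of the time instead of 5%. After a passed proteomics validation it agrees 92-100% of the time whether or not the protein is real. With perfect assay agreement, a true difference of 0.30 SD would be reported as about 0.41 SD, while a difference as large as 0.57 SD is barely distorted (0.60).

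These sizes rest on the assumed number of proteins, independence between proteins, the assay correlation, and selection of single proteins. Weaker assay agreement or fewer proteins makes the optimism smaller; more proteins makes it larger. The direction depends on none of these, provided the two assays are positively correlated in the same patients. The consequence is moderate: an overstated claim of replication and an inflated effect size for the proteins, with a sound independent validation still in the plan.

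**What to change.** In A.4.2, for the protein signature:

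- Define the ELISA validation as the test in the independent 50+50 validation sample only.
- Call ELISA in the discovery sample assay confirmation, as the section already does for cytokines.
- Report the combined 200-patient estimate as descriptive, without a validation p-value.
- State that the proteomics and ELISA validations share the same 100 validation patients, so together they are one independent replication on two platforms.

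No new samples or assays are needed, since plasma from both samples would be assayed by ELISA in any case. The cost is precision: the test uses 100 rather than 200 patients. By the calculation behind B.1.2, the detectable difference at 80% power is 0.57 SD, against about 0.57/√2 = 0.40 SD for 200. Half of that apparent gain comes from patients who cannot serve as independent evidence.

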Project 1--Long-Term Outcomes of Delirium, Leader: [name].: This study will test the hypothesis that delirium will be independently associated with a higher rate of long-term cognitive and functional decline. We will utilize appropriate epidemiologic and statistical approaches to evaluate the impact of delirium on cognitive functioning in our prospective cohort over time, as reflected by our composite summary neuropsychological measure, as well as long-term functional decline and health care utilization. Importantly, these analyses will control for relevant covariables, including age, gender, education, cognitive reserve indicators, APOE-ε4 status, comorbidity, baseline cognitive impairment, and vascular risk factors, on which detailed information will be collected for this study. A sub-study of project 1 will look at the clinical outcomes of delirium, specifically rates of conversion to mild cognitive impairment (MCI) or dementia, among those who demonstrate significant cognitive decline during the study. A validation-study of project 1 will validate phone neuropsych testing with face-to face neuropsych testing. The phone version of the neuropsych testing may be used in the future for patients who are not available for face-to-face interviews. Another sub-study to Project 1 will identify markers of under- and over treated pain and associated adverse outcomes including delirium and prolonged length of stay during the index hospitalization using existing SAGES data and chart review methods to collect additional data.

Project 2--Biomarker Discovery for Delirium, Leader: [name].: The goal of this study is to utilize state-of-the-art methods toward the discovery of plasma biomarkers for delirium. Plasma biomarkers will be assessed at 4 time points for this study: baseline, immediately post-operative, hospital day 2, and one-month follow-up. The Luminex multiplex analyzer system will be used to describe a cytokine “signature” associated with delirium. Mass spectrometry proteomics will be used to describe a plasma protein “signature” for delirium. We will also examine the relationship of the cytokine and protein signatures

with long-term cognitive and functional outcomes following delirium. Finally, we will create a repository of plasma and genetic material, which will be used for future biomarker discovery and validation studies for delirium and other surgical outcomes.

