Delirium may be associated with long-term cognitive impairment and dementia. Previous studies demonstrate that delirium persists much longer than previously believed, with symptoms commonly lasting months to years in some patients (Levkoff 1992, Rockwood 1993, Levkoff 1994, [name] 2000, Cole 2003, McCusker 2003). The entities of persistent delirium (Levkoff 1992, Rockwood 1993, Levkoff 1994, [name] 2000, Cole 2003, McCusker 2003) and reversible dementia (Clarfield 1988) blur the boundaries between these conditions. Some epidemiologic studies have documented an increased risk for long-term cognitive decline in patients with delirium, even after controlling for relevant covariables in some studies (See Table 1); however these prior studies have been contradictory and limited by high attrition rates, infrequent follow-up, inclusion of dementia patients, lack of baseline pre-delirium assessment, lack of follow-up neuropsychological testing, and incomplete control for confounders and competing causes of cognitive decline. Some causes of delirium, such as hypoxia or hypoglycemia, may lead to neuronal death and permanent cognitive sequelae ([name] 1997). In addition, neuroimaging studies demonstrate regions of hypoperfusion in patients with delirium (Yokota 2003, Fong 2006), suggesting that delirium may incite a derangement in brain vascular function that may lead to dementia in some cases. Finally, delirium may herald the onset of dementia in many cases. This phenomenon is well-recognized clinically, where clinicians and family members report that some patients "never return to baseline" after developing delirium. While the underlying causes do contribute to the poor prognosis associated with delirium, current evidence suggests that the development of delirium may independently contribute to these poor outcomes. Given that delirious patients (with associated agitation and lethargy) are at increased risk for aspiration, pressure ulcers, pulmonary emboli, and decreased oral intake, the finding that delirium is associated with worsened outcomes even after controlling for baseline patient characteristics and etiologic factors is not surprising. Thus, delirium may identify patients at high risk for poor outcomes, and may also independently contribute to poor outcomes.

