A.3.2.3.1. Delirium presence: The presence of delirium will be rated by the dichotomous yes/no diagnosis of delirium based on the validated Confusion Assessment Method (CAM) algorithm. This 4-item algorithm will be used to make a diagnosis of delirium based on DSM criteria. It has excellent psychometric properties, and is widely used in both research and clinical settings. The CAM rating will be completed at baseline, daily during each hospitalization, and at each follow-up assessment, based on information from the interview, 3MS (baseline/every 6 mos) or other cognitive screen (daily in hospital), digit span testing, DSI, and MDAS. Delirium by interviewer rating (CAM criteria) will be augmented with delirium rated as present by medical record review during the index hospitalization, since delirium can occur between interviews. For this study, we are assuming a delirium rate of at least 25% for the surgical cohort. We are also assuming that the vast majority of delirium occurs (or at least begins) in the hospital setting; delirium is rare in community settings. The Delirium Symptom Interview (*Albert 1992*) will be used to rate delirium symptoms and is useful to help with the completion of the CAM rating. This is a brief instrument that includes both questions asked directly of the patient and a series of structured observations. It is used specifically to determine the presence or absence of eight key features of delirium, as originally defined by the DSM-III criteria. Use of this method in conjunction with the CAM has been previously described (*Simon 2006*). For hospitalizations during follow-up, a validated chart rating of delirium (*[name] 2005*) will be completed.

A.3.2.3.2. Delirium severity: Delirium severity will be rated with the widely-used Memorial Delirium Assessment Scale (*Breitbart 1997*), a 10-item scale that uses information from the MMSE and structured observations to rate delirium severity. Each item is rated as 0-3, to generate a 0-30 scale (30=most severe).

A.3.2.3.3. Delirium duration and recurrence: Delirium duration will be determined as the total number of delirium-days (as rated by a positive CAM rating) during hospitalization in the

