A.7.1 Subject Selection: Study participants who completed a face-to face neuropsych battery within the last two weeks will be contacted by phone and the purpose and details of the validation-study explained. If the subject agrees to participate, a verbal consent will be obtained over the phone.

A.7.2 Instruments: This validation study will include previously approved neuropsych battery of the main SAGES study (HVLt-R, short cognitive screen (S-COG), Digit Span, Verbal and Category Fluency) and in addition, the Boston Naming Test –Short Form for phone administration and D-KEFS verbal fluency test. It is anticipated that the testing will take no more than 20 -30 minutes to complete.

A.7.3 Outcomes: Results of the phone testing will be validated against the test performed during the face-to face neuropsych testing that is being done every 6 month for the main study. The validation study will reveal if the results of neuropsych test administered over the phone are comparable to face-to-face testing.

A.8. Procedures specific to the Project 1 Pain – Delirium Study

A.8.1 Subject Selection: All surgical patients will be included.

A.7.2 Instruments: This sub-study will use data that has already been collected (demographic data, hospital interview data, chart abstraction) and will also collect additional data from the medical charts of the index hospitalization including detailed medication information and evidence of under-treated (e.g., changes in pain medication dose/type/frequency, patient pain rating, family or medical staff comments) and over-treated pain (e.g., patient lethargy, family and staff comments, reduced dose of pain medication).

A.7.3 Outcomes: This sub-study will identify markers of over- and under -treated pain and the association of these markers with delirium and increased length of stay.

TABLE 2. DESCRIPTION OF STUDY VARIABLES

Variable/Instrument	Source of Information	Purpose
Patient and General Descriptors:		
Demographics	INT, MR	Descriptive; Covariable/confounder
Education/Occupation	INT	Descriptive; Covariable/confounder
Surgical type	MR	Descriptive; Covariable
Cognitive function:		
• Neuropsychological test battery	INT	Primary outcome
• 3MS (Teng 1987)	INT	Screening variable and used to rate delirium
• Digit span test (Cummings 1985)	INT	Used to rate delirium
• Delirium:		
- CAM ([name] 1990)	INT	Major predictor variable (SA1)
- MDAS--delirium severity (Breitbart 1997)	INT	Major predictor variable (SA2)

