To safeguard confidentiality and privacy of protected health information, each study subject will be assigned a unique code number for the study, and the subject's name or identifiers will never be attached to any form, plasma sample, or genetic material. A separate file linking the patient's name with study number and identifiers will be kept in a password-protected data file, accessible only by trained, HIPAA-certified research staff. The data file will be stored on a password-protected server, and will not be stored on any portable media. All study forms will be deidentified kept in secure, locked file cabinets. The study investigators will assume full responsibility to maintain the confidentiality of all data. All study results will be presented only as statistical aggregates that will neither identify nor permit identification of individual subjects. We will follow Medicare/CMS approved data management procedures for storage, access, management, and analysis of the Medicare data. <https://www.instituteforagingresearch.org/resources/research-administration/ifar-research-compliance/data-protection>

If a study interviewer identifies delirium in the course of daily postoperative assessments, we will notify the primary care team by placing a 'flag' on or near the cover of the medical record. The flag will be a bright piece of paper designed and positioned in conjunction with our participating surgeons. It will state that, based on our research assessment, the patient meets Confusion Assessment Method (CAM) criteria for delirium on that day. We will update the flag on a daily basis, and remove it when the patient no longer meets CAM criteria. Since ours is a research-based assessment that will not be performed by a clinician, the flag will not be incorporated into the permanent medical record. Furthermore, our study team will not dictate further evaluation or treatment, which will be conducted at the discretion of the primary care team.

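### In the Pain–Delirium sub-study, chart markers of over-treated pain, lethargy above all, can be signs of delirium or follow it, so their undated association with delirium could arise without any effect of pain treatment.

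*Protocol*

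**What the plan says.** The Project 1 summary in section B1 sets the sub-study the aim of identifying "markers of under- and over treated pain and associated adverse outcomes including delirium and prolonged length of stay during the index hospitalization". Delirium is thus the outcome and pain treatment the exposure.

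Section A.8 includes all surgical patients. Besides data already held, it "will also collect additional data from the medical charts of the index hospitalization". Evidence of under-treatment is illustrated by "changes in pain medication dose/type/frequency, patient pain rating, family or medical staff comments", and the other category by "over-treated pain (e.g., patient lethargy, family and staff comments, reduced dose of pain medication". The outcomes paragraph then promises "the association of these markers with delirium and increased length of stay". No time window and no ordering of marker and outcome is given.

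Three other places bear on this:

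- Section B2, on why delirium has poor outcomes: "Given that delirious patients (with associated agitation and lethargy) are at increased risk" of several complications.
- Section A.3.2.3.1: the interviewer's CAM rating is "augmented with delirium rated as present by medical record review during the index hospitalization".
- Section B.5.2: "If a study interviewer identifies delirium in the course of daily postoperative assessments, we will notify the primary care team", by a flag on or near the chart. Further evaluation and treatment are left to that team.

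**The concern.** An exposure should precede its outcome and be measured separately from it. The markers as described need not do either. Lethargy charted on a day of delirium may be a symptom of the delirium and would still count as evidence of over-treated pain. A dose lowered after delirium was recognised would count the same way. Because part of the delirium rating comes from the record that also supplies the markers, the two measurements are not fully independent.

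Length of stay has a related problem. A patient who stays longer has more chart-days on which a marker can be recorded, so marker-positive patients will tend to have longer stays even if the marker has no influence on discharge.

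At stake is whether the sub-study's stated aim can be interpreted. A positive association between over-treatment markers and delirium could mean that over-treatment leads to delirium, that delirium produces the markers, or both, and the data as described would not separate these. The primary Project 1 analyses of cognitive and functional decline do not use these markers.

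**Working it through.** The protocol states no effect size, test or power for this sub-study, so there is no figure to reproduce. The check is a reading of the text followed by an illustration.

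**How well each route is supported**

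| Route | Support in the protocol |
|---|---|
| Lethargy is both marker and delirium feature | Direct: A.8 against B2 |
| Marker and delirium drawn from one record | Direct that the record is shared (A.8, A.3.2.3.1); whether one note scores both is not shown |
| Dose reduced in response to delirium | Made possible by the B.5.2 flag; not stated |
| Longer stay gives more marker opportunity | Follows from using the whole index stay with no window |

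**Size of a spurious association with delirium**

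From the protocol: 550 surgical patients (B1) and a delirium rate of at least 25% (A.3.2.3.1), taken as 25%. This gives 137.5 with and 412.5 without delirium.

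Assumed: the marker rate without delirium is q = 10% or 20%; true over-treatment is unrelated to delirium; delirium itself makes a delirious patient marker-positive with probability s; two-sided α = 0.05.

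The marker rate in delirious patients is p1 = 1 − (1 − q)(1 − s), and in the others p0 = q. The odds ratio is [p1/(1 − p1)] / [p0/(1 − p0)].

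Worked case, q = 0.10 and s = 0.10: p1 = 1 − 0.90 × 0.90 = 0.19. OR = (0.19/0.81)/(0.10/0.90) = 0.2346/0.1111 = 2.11.

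The chance of p < 0.05 is Φ[(p1 − p0 − 1.96·SE0)/SE1], with pooled SE0 and unpooled SE1. Here the pooled rate is 0.25 × 0.19 + 0.75 × 0.10 = 0.1225. SE0 = √[0.1225 × 0.8775 × (1/137.5 + 1/412.5)] = 0.0323. SE1 = √(0.19 × 0.81/137.5 + 0.10 × 0.90/412.5) = 0.0366. So Φ[(0.09 − 0.0633)/0.0366] = Φ(0.73) = 0.77.

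| q | s | p1 | Spurious OR | Chance of p < 0.05 |
|---|---|---|---|---|
| 10% | 0 | 10% | 1.00 | 5% |
| 10% | 5% | 14.5% | 1.53 | 32% |
| 10% | 10% | 19% | 2.11 | 77% |
| 10% | 20% | 28% | 3.50 | 99.7% |
| 20% | 5% | 24% | 1.26 | 18% |
| 20% | 10% | 28% | 1.56 | 50% |
| 20% | 20% | 36% | 2.25 | 96% |

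With the 500 patients whom B.1.1 expects to undergo surgery, the odds ratios are unchanged and the chances fall slightly (73% instead of 77% in the worked case).

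**Length of stay and unequal follow-up**

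Assume a constant 5% chance per day that a marker is charted, unrelated to anything else. Over 2 days the chance of at least one is 1 − 0.95² = 9.8%; over 5 days it is 1 − 0.95⁵ = 22.6%. Longer stays carry more markers by arithmetic alone.

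The same figures show why simply cutting the marker count at delirium onset is not a repair. With 2 pre-onset days in cases and the full 5 days in non-cases, OR = (0.0975/0.9025)/(0.2262/0.7738) = 0.108/0.292 = 0.37, a spurious protective association with no true effect.

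**The case against.** The best defence is that A.8 is a short description of an exploratory chart review. The markers are given as examples, the word used is association, and no model, score or final definition of over-treatment is fixed. Timing rules commonly sit in an analysis plan that is not shown here. Section A.3.1.4 already schedules daily CAM, DSI and MDAS ratings, so interviewer-rated onset has a date, and the detailed medication information to be abstracted may be dated too.

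Much of that stands. A missing window alone would be a detail for the analysis plan. What goes beyond missing detail is that the protocol chooses as a marker for delirium something that its own background section attributes to delirium. Analysed as described, that choice can build the association in. An analysis rule can repair this only if lethargy and comments are dated at abstraction, on which the text is silent.

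Three stronger readings are tempting, and the protocol does not support them. A reader might infer that doses are lowered because of delirium; B.5.2 only makes this possible and says that the study will not direct treatment. A reader might infer that one chart note scores both marker and outcome; chart review only supplements the CAM, A.3.1.5.5 describes the chart method as validated, and its criteria are not given. A reader might infer that a false association is certain; it depends on s, and at s = 0 the odds ratio is 1.0.

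**Conclusion.** The point holds as a design weakness of one secondary sub-study. The lethargy limb rests on explicit text and carries it alone; the dose-reduction limb is a possibility. A spurious association of over-treatment markers with delirium could appear, with an odds ratio of about 1.3 to 3.5 and an 18% to 99.7% chance of p < 0.05. These figures assume a 10–20% marker rate without delirium and delirium itself producing the marker in 5–20% of delirious patients. The protocol supplies only the 550 and the 25%, so the range shows what modest contamination can do and is not an estimate. The length-of-stay limb follows from the lack of a window; its size cannot be given from the protocol.

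The change should be made before the markers are analysed. Nothing here bears on the primary Project 1 analyses or on how pain should be treated.

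**What to change.** 1. Record the date of each marker at chart abstraction, including lethargy and comments.
2. For delirium, relate markers only to later delirium, with equal opportunity for exposure in cases and non-cases. Either count markers in one fixed early postoperative window, among patients still delirium-free at its end, or use day-by-day risk sets with a time-varying marker and next-day delirium as the outcome, taking onset from the daily CAM dates. Delirium found only by chart review needs a date as well.
3. Keep lethargy out of the primary over-treatment definition when delirium is the outcome, and show the result with it included as a sensitivity analysis.
4. For length of stay, count markers in a fixed early window among patients still in hospital at its end.

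The cost is a little more abstraction and analysis work and fewer countable marker events. The fixed window also drops patients whose delirium begins inside it; the risk-set version retains those whose onset falls after their first day at risk.
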